# D. The data collection and measurement techniques are appropriate and effective

# Experimental Design

The overall research design is a within-group, randomized controlled study to compare analgesic effects between EStim and BreEStim (single-session in Exp 1, long-term intervention in Exp 3), between BreEStim120 and BreEStim240 (Exp2). We prefer this within-group comparison because 1) pain, by nature, is a subjective perception, it is difficult to control (physical, social, psychological) multi-factors between two groups; 2) It will be fair that all subjects receive the innovative intervention, which is superior to regular electrical stimulation according to our pilot data; 3) according to our recent BreEStim study in patients with spinal cord injury, the duration of analgesic effect was 15 hours after one-session of BreEStim treatment. An interval of one week for washout should be sufficient for Exp 1 & 2. The washout interval will be 2 weeks for Exp 3. It is our experience with subjects with spinal cord injury that an interval of 7 days is sufficient for subjects to return to their baseline after BreEStim treatment. (Li et al. 2016; Karri et al. 2018b; Li et al. 2018) However, we did notice that one subject with post-amputation PLP had carry-over effect for one month(Li et al. 2012a). We plan to screen these patients with longlasting carry-over effects. These patients will be excluded from the subject should this happen.

In Experiment 1, we plan to use our recent BreEStim and EStim protocols (Li et al. 2013; Li et al. 2014; Li et al. 2016) to measure mechanical sensation threshold, thermal (cold/warm detection, cold/hot pain) thresholds, and electrical sensation and pain thresholds in the treatment limb and contralateral limb. The same group of subjects will receive both BreEStim and EStim at a randomized yet balanced order with at least 7 days apart. The same amount of electrical stimulation (120 stimuli) will be given during both BreEStim and EStim. The purpose of this aim is to investigate whether BreEStim could have better analgesic effect than EStim in amputee subjects with chronic phantom limb pain as we observed in healthy subjects. We expect increased electrical pain thresholds in both limbs after BreEStim because of its central desensitization effects.

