In Experiment 2, a group of subjects will receive BreEStim at two different doses (120 vs. 240 stimuli) on two different days with at least 7 days apart. The purpose is to compare the extent and duration of analysesic effects between two doses of BreEStim. We expect that BreEStim240 could have similar degree of pain reduction but with longer duration compared to BreEStim120, as shown in our pilot study. Therefore, we expect to use BreEStim240 in Experiment 3 for the long-term intervention.

[figure not shown]

Figure 7: Illustration of study design for Experiments 3

The University of Texas

IRB NUMBER: HSC-MS-20-1032 UTHealth IRB APPROVAL DATE: 12/03/2020

In Experiment 3, the same established protocol will be used (Li et al. 2012a; Li 2013). The effect of two interventions (BreEStim and EStim) will be compared. Each intervention consists of 240 stimuli/session (about 40-50 min/session), 1 session/day for 10 consecutive sessions (over 2 weeks). After a follow-up (wash-out) period of two weeks, the same subject will be treated with the other intervention with a same follow up of 2 weeks. The intensity of stimulation will be adjusted as subjects could tolerate. Electrical stimulation will be delivered to the median nerve on the dominant side. The wash-out/follow-up period of 2 weeks allows removal of accumulative or carry-over effect from the previous intervention.

It is expected that electrical pain threshold will be further increased after BreEStim with parallel reduction in pain perception, while there is no or minimum change after EStim and no significant change in pain perception. Pain threshold will be measured using QST. Pain perception will be characterized by duration and amount of change in pain on visual analog scale (VAS), i.e., how much pain is reduced and how long it lasts. As such the effect of treatment is quantified by reduction x hours.

The secondary outcome measurement will be General Well-Being (GWB) Schedule Survey and Center for Epidemiologic Studies Depression Scale (CES-D), NIMH Survey to examine the possible effect of pain reduction on general well-being, depression and quality of life of the patients. These surveys have been well validated and commonly used (Sherman et al. 1984; Wartan et al. 1997; Kooijman et al. 2000).

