Heart rate variability as objective outcome measurements: We have been searching for noninvasive objective pain outcome assessment. Heart rate variability has been recognized as a physiological marker for pain assessment (Appelhans and Luecken 2008; Karri et al. 2018b; Karri et al. 2019). We will follow our recent experimental procedures (Karri et al. 2018b; Karri et al. 2019) to collect 5 minutes of Heart Rate recordings before and after the interventions.

**Experiment 2** The aim of this experiment is to explore this "dose-response" effect of BreEStim, by comparing the analgesic effects of two doses of single-session BreEStim. The same BreEStim protocol in Exp 1 will be used for Exp 2. In Exp 2, only BreEStim will be used. Two doses of BreEStim (120 vs. 240 electrical stimuli) will be given at least one week apart in a randomized order. Outcome measures, including VAS, QST thresholds, will be recorded pre- and 10 minutes postintervention. Duration of analogsic effect (lasting hours) will also be recorded.

The experimental set-up will be similar to Experiments 1&2. There are two Experiment 3 different interventions - BreEStim and EStim. Each intervention consists of 240 stimuli/session (about 40-50 min/session), 1 session/day for 10 sessions (over 2 weeks, no treatment in the weekends). After a follow-up (wash-out) period of two weeks, the same subject will be treated with the other intervention with a same follow-up of 2 weeks. The intensity of stimulation will be increased gradually as patients could tolerate. Aversiveness of electrical stimulation is part of treatment strategy. During EStim, a single-pulse electrical stimulation is delivered to the forearm through surface electrodes randomly, while electrical stimulation is triggered by volitionally effortful inhalation during BreEStim as in Exp 1.

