# 6. Data Collection and Analysis

Data collection details have been described above. Data analysis is described here.

**Experiment 1** Repeated-measures two-way ANOVA tests with factors INTERVENTION (2 levels, BreEStim and EStim) and TIME (pre- and post-intervention) will be tested on dependent variables, including VAS, QST thresholds (tactile, electrical, and thermal), to determine statistical significance between two interventions. Paired t-tests will be used to compare the duration of lasting hours between two interventions. p value is set at 0.05. As observed in the pilot data, we expect that BreEStim could have central desensitization and analgesic effects on patients with phantom limb pain, but no such effect after EStim. These findings would suggest that the central desensitization effect of BreEStim could be translated to analgesic effects in patients with PLP. Furthermore, the findings of analgesic effects along with desensitization effects in patients with PLP support central sensitization as a plausible mechanism that mediates post-traumatic PLP.

Experiment 2 Similar to Exp 1, repeated-measures two-way ANOVA tests with factors INTERVENTION (2 levels, BreEStim 120 vs. 240) and TIME (pre- and post-intervention) will be tested on dependent variables, including VAS, QST thresholds (tactile, electrical, and thermal), to determine statistical significance between two interventions. Paired t-tests will be used to compare the duration of analgesic effect (lasting hours) between two interventions. p value is set at 0.05. As shown in the pilot data, we expect that BreEStim could have dose-dependent effects on the duration but not the degree of analgesic effects. These results also suggest that BreEStim could have cumulative effects if patients receive interventions repeatedly over a period of time.

In Experiment 3, Repeated-measures two-way ANOVA will be performed to determine statistical significance between two interventions. Factors include INTERVENTION (BreEStim vs. EStim) and TREATMENT (Pre- and Post-intervention, and Followup). Variables are VAS and modified VAS and QST parameters, GWB, and CES-D. It is hypothesized that the effect of pain reduction is greater in BreEStim than in EStim for amputation patients, manifested by pain reduction on VAS assessment and parallel change of increased electrical pain threshold as shown by pilot data in Experiments 3. Furthermore, pain reduction is accompanied by improvement in general well-being and mood.

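### Experiment 3 uses one two-week interval as both follow-up and washout, and its visible analysis has no period or sequence term and no carry-over-free comparison; carry-over at day 14 is possible but not shown

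*Combined protocol and SAP*

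**What the plan says.** **Design.** The Experimental Design section (4.D) describes the study thus: "The overall research design is a within-group, randomized controlled study to compare analgesic effects between EStim and BreEStim". The same sentence goes on to name the long-term intervention of Experiment 3. Each course is ten sessions of 240 stimuli over two weeks. The Experimental setup section adds: "After a follow-up (wash-out) period of two weeks, the same subject will be treated with the other intervention". So the window that follows the first course is also the run-in to the second.

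**Washout.** For this interval the protocol says "The wash-out/follow-up period of 2 weeks allows removal of accumulative or carry-over effect from the previous intervention". The support in Experimental Design is 15 hours of relief after one session, and the experience that "an interval of 7 days is sufficient for subjects to return to their baseline after BreEStim treatment". Both come from spinal cord injury. The same paragraph reports that "one subject with post-amputation PLP had carry-over effect for one month".

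**Safeguard.** "We plan to screen these patients with longlasting carry-over effects. These patients will be excluded from the subject should this happen". No threshold or timing is given, and the rule is not among the seven exclusion criteria in section 5, Human Subjects.

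**Analysis.** For Experiment 3, section 6 plans a two-way repeated-measures ANOVA: "Factors include INTERVENTION (BreEStim vs. EStim) and TREATMENT (Pre- and Post-intervention, and Followup". It lists no period term, no sequence term, no comparison of the second baseline with the first, and no first-period analysis.

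**The concern.** The visible evidence for a clean washout is indirect. It comes from another condition, and the 15-hour figure is for a single session, whereas Experiment 3 gives ten sessions and the protocol expects effects to accumulate over them. The one long carry-over reported in the target population, about a month, exceeds the 14 days allowed. The background, apparently on the same patient, says the pain came back at 28 days after an accidental stimulation.

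If some BreEStim effect remains when EStim starts, the EStim baseline of BreEStim-first patients is too low. The EStim change, and so the difference between interventions, is then mismeasured. The planned model offers no way to see this and no estimate that is free of it.

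The safeguard brings a problem of its own. Carry-over can be seen only after BreEStim has been given, so the rule would by inference act after treatment has started and would select on response.

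**Working it through.** **What can be reproduced.** The plan gives no residual fraction, and the visible text has no effect size or power behind the 30 subjects of Experiment 3, so there is no plan figure to reproduce. Everything below is illustration under stated assumptions.

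**Inputs.** Pilot VAS reductions for Experiment 1 (three patients, single session): BreEStim 5.3 - 3.2 = 2.1 (B); EStim 4.9 - 4.1 = 0.8 (E). The true difference is taken as D = 2.1 - 0.8 = 1.30. Sequences are 15 and 15 (30 subjects in section 5; balance and no dropout assumed). Let r be the fraction of effect left at period-2 Pre and r2 the fraction left at period-2 Post. For r2 there are three cases: geometric fading (r2 = r squared), lost during period 2 (r2 = 0), and constant (r2 = r).

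**Which contrast.** Section 6 does not name the deciding test for Experiment 3. The Experiment 1 power text uses the intervention-by-time interaction on change in VAS, Experimental Design quantifies pain reduction, and the Experiment 3 hypothesis is a greater reduction. All of these point to change from own-period baseline, so that is what is modelled.

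**Bias formula.** In BreEStim-first patients the measured EStim reduction is E - B(r - r2). If EStim also carries over, the measured BreEStim reduction in EStim-first patients is B - E(r - r2). Averaging the two sequences:

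- only BreEStim carries over: bias = 0.5 x 2.1 x (r - r2) = 1.05(r - r2);
- both carry over in proportion: bias = 0.5 x (2.1 - 0.8) x (r - r2) = 0.65(r - r2).

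**All patients carry over.**

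| Case | r | Only BreEStim | Both |
|---|---|---|---|
| Geometric | 0.25 | 1.05 x 0.1875 = 0.197 (+15%) | 0.65 x 0.1875 = 0.122 (+9%) |
| Geometric | 0.50 | 1.05 x 0.25 = 0.263 (+20%) | 0.65 x 0.25 = 0.163 (+13%) |
| Lost | 0.25 | 1.05 x 0.25 = 0.263 (+20%) | 0.65 x 0.25 = 0.163 (+13%) |
| Lost | 0.50 | 1.05 x 0.5 = 0.525 (+40%) | 0.65 x 0.5 = 0.325 (+25%) |
| Constant | either | 0 | 0 |

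**Only a subgroup carries over** (BreEStim residual only, r = 0.5). A fraction f has effect L, with the overall mean held at 2.1; bias = 0.5 f L (r - r2).

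- f = 0.1, effect 1.5 times the rest: others 2.1/1.05 = 2.0, L = 3.0. Bias 0.0375 (+3%) geometric, 0.075 (+6%) lost.
- f = 0.2, effect twice the rest: others 2.1/1.2 = 1.75, L = 3.5. Bias 0.0875 (+7%) geometric, 0.175 (+13%) lost.

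**Excluding the long responders**, same subgroups. The rest have true differences 2.0 - 0.8 = 1.20 and 1.75 - 0.8 = 0.95.

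- Dropped from the BreEStim-first sequence only: (13.5 x 1.20 + 15 x 1.30)/28.5 = 1.25 (-4%) and (12 x 0.95 + 15 x 1.30)/27 = 1.14 (-12%).
- Dropped from both sequences: 1.20 (-8%) and 0.95 (-27%).

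**Omitted period term.** With equal sequences it causes no bias but costs precision. In simulation (15 and 15, paired effect 0.5 SD, assumed period effect 0.5 SD of the paired difference) power was 0.67 without the term and 0.75 with it. With unequal sequences the contrast shifts by p(n2 - n1)/(n1 + n2). For an assumed trend p of 0.5 points, 13.5 against 15 gives 0.5 x 1.5/28.5 = 0.03, and 12 against 15 gives 0.5 x 3/27 = 0.06 points (2% to 4% of 1.30).

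**How plausible is r?** If the 26.1-hour mean relief after one 240-stimulus session (Experiment 2 pilot) is borrowed as a half-life, 0.01% remains after 14 days. Residuals of 25% and 50% need half-lives of 7 and 14 days. The documents do not settle which is closer after ten sessions.

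The protocol's reduction-times-hours measure was not modelled.

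**The case against.** The protocol did consider carry-over. Two weeks is 336 hours, about 13 times the 26.1-hour mean relief after one 240-stimulus session and twice the 7-day experience. It discloses the one contrary case, which is a single patient, and plans a safeguard. Aim 3 is worded over the two-week treatment course. Change from own-period baseline cancels a constant residual, and a missing period term causes no bias with equal sequences. A first-period comparison has less precision. Finally, the text between the Experiment 2 sample-size paragraph and the design section, and Figure 7, were not available. Section 6 refers to "parallel change of increased electrical pain threshold as shown by pilot data in Experiments 3", so evidence for the washout may be there.

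Most of this stands, and it is why carry-over is called possible and no more. It does not dispose of the point. Single-session relief does not show what remains after ten sessions that are expected to accumulate. The own-baseline contrast is not protected if the residual fades during period 2. The safeguard, as written, selects on response.

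**Conclusion.** The point holds as a gap in the analysis plan that should be closed, with medium confidence. The double use of the interval, the two-factor model and the undefined exclusion are plain in the text. Any bias in the BreEStim-minus-EStim contrast depends on residuals the documents do not give. Assumed values produce +3% to +13% if 10% to 20% of patients carry over. If all do, with 25% to 50% left, they produce +9% to +25% when both interventions carry over in proportion, or +15% to +40% when only BreEStim does. A constant residual gives zero. The exclusion rule works the other way, at -4% to -27%.

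A reader might infer more, but the documents do not support it:

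- *That the washout fails.* One case and an expectation of accumulation do not show this.
- *That the improvement in baseline pain after BreEStim, which the protocol treats as grounds for a further trial, is contaminated.* That is a change within BreEStim. In BreEStim-first patients all period-1 readings precede the second course. In EStim-first patients only EStim residue could matter, and pilot EStim relief lasted 2.0 hours.
- *That BreEStim would be understated through a comparison of Post scores.* Nothing visible makes that the deciding test.
- *That order is not randomised in Experiment 3.* Experimental Design names Experiment 3 within the randomised design. Only an explicit statement of balanced order is missing.

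**What to change.** 1. Add period and sequence to the Experiment 3 model, and name INTERVENTION x TREATMENT on change from own-period Pre as the deciding contrast. TREATMENT has three levels, so say whether Post or Followup decides. The period term protects precision and guards against unequal sequences; it does not remove carry-over. State that order is balanced.
2. Keep all treated patients in the analysis, including those with long carry-over, and report any exclusions by sequence. Reconcile the exclusion rule in Experimental Design with the criteria in section 5, including its threshold and timing.
3. Report period-2 Pre minus period-1 Pre by sequence with a confidence interval, and do not use it as a gate. With 15 patients and an assumed SD of 1.5 the half-width is 0.83 points. Power is 7% to 14% for the subgroup shifts (0.15 to 0.35 points) and 24% to 71% if all patients carry over, so a non-significant result would not show washout.
4. Prespecify a period-1-only ANCOVA on period-1 Pre, for Post and for Followup, as a sensitivity analysis beside the crossover.

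**Cost.** Visits and treatment are unchanged; the edits are to analysis, design and eligibility text. The period term costs one degree of freedom. The period-1 comparison is between patients: with 15 per sequence its 95% half-width is about 2.05 x sqrt(2/15) = 0.75 SD unadjusted, or 0.65 to 0.54 SD with an assumed Pre-Post correlation of 0.5 to 0.7. In simulation (between-patient SD 1.5, within-patient SD 1.0, geometric fading, all assumed) its root-mean-square error was 0.48 to 0.52, against 0.38 to 0.45 for the crossover at Post. The crossover was worse only at Followup with all patients carrying over and half the effect left (0.53). The crossover should stay the main analysis and the period-1 estimate should be supportive only.

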# **Experimental setup (BreEStim and EStim protocols and measurement)**

Experiment 1 We plan to use our recent BreEStim and EStim protocols (Li et al. 2013; Li et al. 2014). Briefly, subjects will be seated comfortably with the arm on the experimental table (Fig 8). Subjects will wear a facemask that will be connected to a Pneumotach system to record breathing signals and to prevent hyperventilation. Surface electrodes will be trimmed to be applied to the median nerve ipsilateral to the affected side proximal to the wrist line (see Fig 8). Note that important acupuncture points (Neiguang and Waiguan) are located beneath the electrodes. So these points will be stimulated during both BreEStim and EStim).

[figure not shown]

Figure 8 Experimental settings. On the right panel, an electrical stimulus (Lower) is triggered when the airflow rate (Upper) of a forceful inhalation reaches 40% of its maximum value.

The University of Texas

In the BreEStim treatment, a single-pulse electrical stimulus is delivered to the nerve when patients are taking fast, strong, and deep inhalation, similar to a deep breath but faster and stronger. Voluntary inhalation plays an important role in this intervention. Voluntary inhalation is defined as effortful deep and fast inhalation. Subjects are instructed to take a deep breath, similar to routine deep breaths, but faster and stronger, usually involving obvious expansion of chest wall. It has been reported that there are respiratory specific connections between the insula and the activity of pulmonary stretch receptors (Gaytan and Pasaro 1998; Hanamori et al. 1998). Experimentally, the airflow rate is monitored online. When the airflow rate reaches 40% of its peak, an electrical pulse is triggered (Li et al. 2012a; Li 2013). The frequency of BreEStim generally varies. As in our previous series of BreEStim experiments, subjects are usually comfortable to continue voluntary breathing for 20 – 30 electrical stimuli without a break. As seen in Figure 8, BreEStim is delivered at about every 2 seconds. The single-pulse electrical stimulus is a square wave with a width of 0.1 ms. The intensity is set where subjects feel painful but yet tolerable, equivalent to 7 on the 0-10 VAS scale. When wearing a face mask, subjects usually tolerate such breathing very well. No hyperventilation has been reported (Li et al. 2012a; Li 2013).

In the EStim condition, subjects will also wear the face mask as in the BreEStim condition. The main difference is that subjects will be breathing automatically and comfortably and electrical stimulation pulses will be delivered randomly. The pulses will be programmed to randomly deliver at about every 2 seconds (between 1.9 seconds and 2.1 seconds). The pulse width will be the same at 0.1ms. Similarly, subjects control the intensity of electrical stimulation. For both BreEStim and EStim, they are strongly encouraged to increase the intensity to be painful yet tolerable gradually from their pain threshold. The level of pain with painful stimulation will be 7 on the 0-10 VAS scale. The purpose is to make the intensity of electrical stimulation comparable between two conditions. According to previous studies, the intensity is comparable between BreEStim and EStim(Li et al. 2013; Li et al. 2014). The intensity of electrical stimulation will be recorded during the course of treatment.

Two interventions (BreEStim vs. EStim) will be given to the same subject on a different day with at least 7 days apart. As in previous studies(Li et al. 2013; Li et al. 2014), a total of 120 electrical stimuli will be delivered for each intervention. The order of interventions will be randomized and balanced across subjects. Both interventions will be given at the same time of the day, as determined by subject's schedule. It is important to emphasize that subjects will be explicitly instructed to maintain the same pain regime even they feel that treatment has helped in pain reduction, such that pain reduction is mainly related to BreEStim or EStim.

**Outcome measurement includes visual analogue scale (VAS) and Quantitative Sensory Testing (QST) and Hear rate variability (HRV).** The VAS method has been extensively used and validated (McCarthy et al. 2005). Using VAS to rate pain intensity has been considered a standardized measurement to evaluate effectiveness of deep brain stimulation for pain management in a multi-center study by Medtronic (Medtronic, Minneapolis, MN). These results have been reported to US Food and Drug Administration for judgment on the efficacy of pain management(Coffey 2001). In the project, we plan to use a modified VAS to quantify pain reduction. As used in our pilot study (Li et al. 2012a; Li 2013), the effect of pain reduction is characterized by duration and amount of change in pain on VAS, i.e., how much pain is reduced and how long it lasts. As such the effect of treatment is quantified by reduction×hours. The effect and the intensity of stimulation will be recorded daily during the course of treatment. For VAS, the duration of analgesic effect from the intervention will also be recorded. VAS scores will be obtained before and 10 minutes after. Post-intervention VAS will be also assessed through follow-up phone calls every 4 hours except night time (10pm – 7am). It is important to emphasize that subjects will be explicitly instructed to maintain the same pain medication regimen even if they feel that treatment have helped in pain reduction.

QST includes tactile sensation threshold (TST), electrical sensation threshold (EST), electrical pain threshold (EPT), and thermal thresholds. VAS and QST will be recorded immediately before and 10 minutes after the interventions. In this experiment, we aim to test the central de-sensitization effect of BreEStim. To standardize QST (Li et al. 2015), all thresholds will be measured only on the residual limb at 5 cm above the distal residual limb. The symmetrical site on the contralateral limb will also be localized. After the target areas are localized and marked with a marker, subjects are instructed to stay relaxed in a chair with arms and legs comfortably supported in a symmetrical position. The order of QST will be randomized and balanced across testing sites. The following measurement will be made.

UTHealth IRB APPROVAL DATE: 12/03/2020
The University of Texas
Houlth Science Conferral Houston

16

Tactile sensation threshold: Tactile sensation threshold will be tested using Von Forey filaments (Touch-Test Sensory Evaluator, North Coast Medical Inc.). The center of the thenar eminence/testing sites on the leg will be marked with a pen symmetrically on both hands. Subjects will be instructed to close their eyes. The experimenter will press the filament at a 90° angle against the marked area until it bows for approximately 1.5 seconds and then removed. Testing will begin with the thinnest 1.65 filament, then progresses to the next monofilaments. An explicit response of touch sensation is defined as tactile sensation threshold.

Electrical sensation and pain thresholds: The same trimmed electrodes will be used to examine electrical sensation threshold and electrical pain thresholds (electrical stimulator 7SA, Digitimer). A pair of electrodes is placed next to each testing site. For electrical sensation threshold, the intensity of electrical stimulation will start from zero and gradually increase in steps of 0.1 mA. Similarly, subjects will be instructed to close their eyes and to say "yes" when they explicitly feel electrical stimulation. Three repetitions will be made and the average will be used as the electrical sensation threshold. Electrical pain threshold is then measured. The intensity of electrical stimulation will start from the sensation threshold level and increase in steps of 1 mA. The electrical pain threshold is reached when subjects first feel electrical stimulation painful. To improve consistency among subjects, they are advised that the pain threshold level is equivalent to 1 on the 0-10 VAS scale. Similarly, the average of three tests will be used as the electrical pain threshold.

Thermal thresholds: Thermal thresholds (warm sensation, cold sensation, heat pain, cold pain) will be examined using a Medoc PATHWAY system. The established "Limits Full Series" protocol will be selected. Briefly, the protocol contains a series of tests in the following order: 4 tests of cold sensation threshold, 4 tests of warm sensation threshold, 3 tests of cold pain threshold, and 3 tests of heat pain threshold. The 30x30 ATS probe is secured with its center on the testing. Subjects will have an education session prior to the protocol. The averaged value will be used for each threshold.

Heart rate variability as objective outcome measurements: We have been searching for noninvasive objective pain outcome assessment. Heart rate variability has been recognized as a physiological marker for pain assessment (Appelhans and Luecken 2008; Karri et al. 2018b; Karri et al. 2019). We will follow our recent experimental procedures (Karri et al. 2018b; Karri et al. 2019) to collect 5 minutes of Heart Rate recordings before and after the interventions.

**Experiment 2** The aim of this experiment is to explore this "dose-response" effect of BreEStim, by comparing the analgesic effects of two doses of single-session BreEStim. The same BreEStim protocol in Exp 1 will be used for Exp 2. In Exp 2, only BreEStim will be used. Two doses of BreEStim (120 vs. 240 electrical stimuli) will be given at least one week apart in a randomized order. Outcome measures, including VAS, QST thresholds, will be recorded pre- and 10 minutes postintervention. Duration of analogsic effect (lasting hours) will also be recorded.

The experimental set-up will be similar to Experiments 1&2. There are two Experiment 3 different interventions - BreEStim and EStim. Each intervention consists of 240 stimuli/session (about 40-50 min/session), 1 session/day for 10 sessions (over 2 weeks, no treatment in the weekends). After a follow-up (wash-out) period of two weeks, the same subject will be treated with the other intervention with a same follow-up of 2 weeks. The intensity of stimulation will be increased gradually as patients could tolerate. Aversiveness of electrical stimulation is part of treatment strategy. During EStim, a single-pulse electrical stimulation is delivered to the forearm through surface electrodes randomly, while electrical stimulation is triggered by volitionally effortful inhalation during BreEStim as in Exp 1.

